## **Ridge Preservation with Hardening Calcium Phosphate Bone Substitutes and Resorbable Membrane for Implant Site Development on Non-containable Extraction Sites: A Clinical and Histological Prospective Case Series in Humans.**

[name], [name]

Tooth extraction is one of the most widely performed procedures in dentistry today and it has been well documented that this affect dimensional changes of the alveolar ridges. Oral rehabilitation with dental implant prostheses can provide more variety of treatment options to patients since high survival rate of implant therapy is well documented. The obstacles that all clinicians have dealt with is how to manage extraction sites to prepare better site for the future dental implant placement or to minimize ridge shrinkage for a fixed or removable prosthesis delivery. Excellent functional and esthetic restoration of an implant largely depends on its placement in an ideal location that will achieve the restorative goals. If management of the extraction site was performed inadequately, the resulting shrinkage of the ridge dimension can require additional ridge augmentation prior to implant placement. That results in prolonged treatment time, multiple additional invasive surgery, and increasing cost for patients. The key processes of tissue modeling and remodeling following extraction have been well documented in both animal [1, 2] and human models. [3, 4] In a dog model, Araujo showed that the buccal bone plate was considerably thinner than the lingual plate, and that horizontal resorption may also cause vertical reduction of the buccal wall. Also sequenced histology suggested that the resorption on the buccal and lingual bone of the extraction site occurred in two types of phases. The bundle bone resorption initiated and the resorbed area was replaced with newly formed woven bone in the first phase. This is because that the bundle bone lost blood supply from periodontal ligament and the lack of blood supply causes vertical bone loss too. In following the first phase, bone remodeling and resorption initiated from the outer surfaces of both bone walls.[1] A human study by Schropp reported that, with regard to the width of the ridge, a reduction of up to 50% was found in 12 months after extraction, of which two thirds occurred during the first 3months of healing period. [5] A systematic review written by Tan assessed the magnitude of dimensional changes for the hard and soft tissues of the alveolar ridge dimensions up to 12 months after the extraction site in humans. Twenty studies were included in the review, and the authors concluded that human reentry studies showed loss of horizontal dimension of 29% to 63% and vertical loss was 11% to 22% following 6 months tooth extraction. These studies demonstrated rapid resorptions in the first 3 to 6 months, and followed by slow rate of reductions for longer time period.[6] Alveolar ridge preservation is a simple procedure aimed at preventing or minimizing dimensional changes following tooth extraction to provide an adequate volume and quality of bone for dental implant placement. Extraction sites treated with ridge preservation have been documented well to have less horizontal and vertical dimensional change as well as increased vital bone formation compared to controls not treated with ridge preservation procedures. [7-12] Ten Heggeler [13] performed a systematic review on the effectiveness of socket grafting procedures at the time of extraction in non-molar teeth in human. The results of this review showed that for ridge preservation procedure, the outcome with the freeze-dried bone allograft group revealed the best in terms of height gain, however, a loss in width of 1.2mm was inevitable. Socket/ridge preservation may contribute to reducing of the ridge dimensional changes after a tooth is extracted. However, they cannot fully prevent the bone resorption because, depending on the technique, on the basis of the included papers one may still expect some loss in three dimensionally. Systematic reviews by Horvath [14], Morjaria [15] concluded

similar results from previous systematic reviews that post-extraction three dimensional changes with ridge preservation therapy might be limited, but cannot be completely eliminated by grafting procedures. Horowitz [12] concluded in his review that the scientific evidence from all of these systematic reviews suggested that socket/ridge preservation techniques contributes to significant benefit with reducing horizontal bone loss of the alveolar ridge. Nonetheless, ridge dimension is important for future implant placement, grafting procedure on the socket at the time of extraction may be very important.

Alveolar ridge preservation adjunct with extraction of teeth can be achieved successfully using a many types of materials such as autografts, allografts, xenografts, and alloplasts. In the past several decades, along with the increasing popularity of implant therapy, the use of graft materials and techniques for alveolar ridge preservation has been studied well. Vignoletti [16] conducted a systematic review regarding surgical protocols for ridge preservation after extractions. This review article revealed that the potential benefit of socket preservation therapies was demonstrated. These grafted procedures resulted in significantly less both vertical and horizontal shrinkage of the alveolar ridge dimensions compare to without grafting procedures. However, the scientific evidence did not determine the guidelines in which type of biomaterial or surgical procedure shows the best outcome for ridge preservation. Hammerle [17] summarized the biology and treatment of extraction and ridge preservation procedures based on the reviews. The variety of materials used in the extraction socket was evaluated in the clinical studies, this review paper did not show any significant differences between materials except collagen plug alone, which caused negative outcomes.

Autogenous (as block or particulate form) bone grafts has been considered as a gold standard for ridge augmentation procedures, however, donor site morbidity associated with block harvest has taken more attentions to concern the second surgical area, and the amount of autogenous graft is limited.[18] For those reasons above, the use of autogenous graft from second surgical site for alveolar ridge preservation procedures remain questionable.

Allografts have been widely used for various regenerative treatment including ridge augmentation and grafting around the periodontal involved teeth. Allografts, especially Freeze-Dried Bone Allograft (FDBA) are generally considered to possess primarily osteoconductive properties. On the contrary, Demineralized freeze-dried bone may also exhibit osteoinductive properties, but this varies with each donor and each tissue bank, and it may even vary between batches within the same bank. [19, 20] However, some patients do not want to have allograft material implanted into their body because of some cultural, religious, and/or psychological reasons due to the nature of the process and source of allografts. As matter of fact, still now, in many countries and regions, allografts have not been official approved by their own FDA (Food and Drug Administrations).

Xenografts have been used with good outcomes in oral regenerative procedures, such as ridge augmentation and sinus graft procedures. The use of deproteinized bovine bone mineral (DBBM) has been well documented. This material has been shown to maintain their natural microporous structure following process in the factory, so that it conducts cell proliferation, migration and new blood vessel formation. The characteristic of the large internal surface enables more contact surface with new bone area and a crystalline structure. This advantage allows the graft material to integrate into the natural bone remodeling process.[21, 22] However, due to the slow resorption rate, many histologic studies

have shown the presence of graft remnants from implanted site even following months after the grafting.

Alloplastic bone substitutes have been used extensively for regeneration and preservation of alveolar ridge in extraction socket. Ideally, these materials are biocompatible; otherwise, the implant will be encapsulated by a fibrous tissue, and lead to a device failure and requirement of a second operation. The variety types of bioactive ceramics have been developed and are clinically used in the daily practice, such as hydroxyapatite (HA), tricalcium phosphate (TCP), HA/TCP biphasic ceramic, and bioactive glass. Calcium phosphates possess osteoconductive ability, and excellent biocompatibility, presumably due to their similar chemical and crystal structure to natural bone minerals.[21, 23-25] The use of  $\beta$ -TCP as a graft material following tooth extraction to preserve the socket dimensions has been reported in few clinical studies. [21, 26, 27] Araujo demonstrated the early healing process of an extraction socket with  $\beta$ -TCP in canine model. The healing site involved the formation of a coagulum, granulation tissue and a provisional matrix, and woven bone formation in those area.[26] From a clinical stand point, bone graft substitutes should be moldable during application, display a self-stabilizing and hardening potential, and form a stable, but still porous scaffold in the defect. This approach would ease the clinical application and, would greatly reduce the need for membranes to retain loose graft materials in the defect, resulting in shortened and simplified surgical procedures. Schmidlin [23] evaluated regenerate potential of hardening polylactide coated  $\beta$ -tricalcium phosphate (TCP) (easy-graft®) in the calvarial bone in rabbits compared to hardening polylactide-coated biphasic calcium phosphate (BCP), and deproteinized bovine bone matrix (DBBM). The authors found that all tested materials showed good biocompatibility. Semi-quantitative analysis and pairwise comparison suggested that BCP showed better efficiency to form centripetal bone compared to  $\beta$ -TCP. After 4 weeks, significantly bone formation in the  $\beta$ -TCP or BCP sites was found compared with the non-grated sites. There was no sign of biodegradation in the BCP and DBBM sites, on the other hands, the  $\beta$ -TCP showed partial resorption after 16 weeks. Leventis [28] showed a case report with an alloplastic in-situ hardening bone substitutes (GUIDOR® easy-graft® CLASSIC, Sunstar). Following extraction and thorough debridement and rinsing with sterile saline, easy-graft® was utilized in the socket. It consists of  $\beta$ -TCP granules, which are coated with polylactic-co-glycolic acid (PLGA). The granules are mixed in a syringe with the provided BioLinker® (N-methyl-2-pyrrolidone solution, Sunstar). Upon contact with blood or saliva the graft granules adhere to each other forming a sticky, easy-to-handle, moldable mass that begins to harden. The grafted socket was left uncovered in order to heal secondary intention. At re-entry 4 months, the post extraction site was filled with newly formed bone. Residual graft material was slightly visible and embedded in the newly formed tissue. An implant was placed with satisfactory insertion torque, and restored after 3months implant placement. The author concluded that the in-situ hardening property of this material may enable clinicians to utilize a flapless procedure without primary wound closure the reduced patient morbidity, preserving the attached keratinized tissue and allowing for further production of keratinized tissue. However, the average of buccal bone thickness on the anterior esthetic area on both maxillary and mandibular arches is very thin. The mean of buccal bone thickness on the anterior area was 0.3mm to 2.09mm. [29, 30] Spray et al reported that a minimal width of 2mm of the buccal bony wall is a prerequisite to maintain the vertical dimension of the alveolar crest following implant placement. Additional surgical procedures such as soft and hard tissue augmentation will be needed to obtain optimal esthetical and functional outcomes. [31] At the time of extraction, even minimal traumatic extraction was utilized, buccal bone fracture could happen. Also those thin buccal bone might be resorbed due to chronic or acute inflammation such as periodontitis, or trauma, tooth fracture, endo-

related lesions. Once buccal bone is missing due to any reasons at the time of extraction, simultaneous ridge preservation and augmentation with bone substitutes and guided barrier membranes. [8, 9]

In previous studies, the change of ridge dimensions were measured with probe by using reference points during procedures. UNC probe only has 1mm measurements, and literature suggested the inaccuracy of evaluation of ridge dimension change. Shneider evaluated that the accuracy of the digital determination of gingival recession and papilla height on virtual jaw models, given the hypothesis that they show lower interrater variability than conventional linear measurements taken clinically or on cast models. They found that the use of digital technologies by intraoral scanning or scanning of cast models improved the reproducibility and lowered the variance of measurements within one individual and between different investigators.[32]

To our best knowledge, there is no study was performed to investigate the combination of GUIDOR® bioresorbable matrix barrier and GUIDOR® easy-graft® for extraction ridge preservation procedures for non-containable sockets in non-molar sites. Thus, the purpose of the current study is to clinically (primary outcome) and histologically (secondary outcome) evaluate alloplastic in-situ hardening bone substitutes (GUIDOR® easy-graft® CLASSIC, Sunstar) and resorbable membrane (GUIDOR® bioresorbable matrix barrier) in alveolar ridge preservation following extraction of non-molar teeth with non-containable extraction sockets. In addition, those dimension change will be measured digitally scanned cast to evaluate the accuracy of the measurements, and cone beam computed tomography.

## **Material and Methods**

The Institutional Review Board of the Indiana University School of Dentistry, Indianapolis, Indiana will review and approve the protocol prior to this study. All participants will provide written informed consent before treatment and will be given a copy of the signed informed consent documents. Up to twenty subjects who have been diagnosed with a need of extraction of single tooth followed by ridge preservation will be recruited to the study.

The procedures listed below including the combination use of the two alloplasts are all within standard care for a tooth extraction with regenerative therapy to preserve the ridge dimensions following extractions with the exceptions of:

- The CBCT (one or more) taken immediate following extraction to evaluate the dimensions of extracted ridge.
- The second CBCT if the subject is not receiving implant therapy.
- The core biopsy (only conducted on those receiving implant therapy)

No data collected for this study will be taken from sources outside of those mentioned above and that are already recorded for standard of care procedures.

Inclusion/Exclusion Criteria,

The following site inclusion criteria will be used: 1) adequate restorative space for a dental implant restoration, if the subject decides previous to study participation that they would like an implant. Note,

agreement to implant placement is not a requirement of the study; 2) minimum of 10-mm vertical bone without impinging on adjacent vital structures (Maxillary sinus, neurovascular bundles); 3) single-rooted tooth to be extracted; 4) ASA class I or II; 5) age >18 years old; 6) subjects who had >50% of height on any portion on the buccal wall of dehiscence and/or fenestration of the extraction socket following extraction will be included from this study; 7) adjacent teeth to extraction site will be present during healing period 8) willingly sign informed consent and authorization. The following exclusion criteria will be used: 1) did not meet any inclusion criteria; 2) pregnancy or nursing woman; 3) subjects with active systemic or localized infection (exclude chronic periodontitis); 4) subjects with a history of any medical conditions that contraindicated or weighed against dental implant placement such as history of bisphosphonate drug use, chemotherapeutic or immunosuppressive agents, autoimmune disease, or poorly controlled diabetes (HBA1c>7%), and 5) subjects with smoking habit (more than 10 cigarettes per day). [33, 34]

### **Continuance Criteria**

Continuance criteria will be updated at each visit to determine subject's eligibility to continue in the study. Continuance criteria questions will encompass the exclusion criteria with the exception of Exclusion Criteria # 1, 3, 4 and 7 are not being captured. Adverse events resulting from responses to the continuance criteria questions will be addressed and documented accordingly. Issues with subjects who do not meet the continuance criteria will be addressed and the PI will determine the subject's ability to continue in the study.

### **Removal of Subjects from the Study**

Subjects may withdraw from the study at any time for any reason. The Investigator may also remove subjects from the study at any time. The Investigator will document the reason for withdrawal for any discontinued subjects. Subjects withdrawn for medical reasons will be referred to a physician/dentist by the study personnel and will have their condition monitored to resolution or until deemed clinically non-significant.

### **Surgical Protocol**

Silicone impressions will be taken for all participants prior to extractions and study models will be made for the purpose of obtaining clinical measurements. Intravenous conscious sedation will be administered at the discretion of the surgeon and the patient request. No pre-surgical antibiotics will be provided and all subjects will receive a single dose of 600 mg ibuprofen before extraction unless patients have some restrictions.

After local anesthesia, the tooth will be extracted in a minimally traumatic manner with periotomes and the socket will be thoroughly debrided. Envelop design (No vertical incision) minimal flap was reflected more than 3mm beyond the alveolar crest. Following extraction, the socket will be examined for defects. If the site meets the inclusion criteria, GUIDOR® bioresorbable matrix barrier will be trimmed and utilized over the socket to cover the defect edge at least 2 mm of edge. Alveolar ridge preservation using the material (GUIDOR *easy-graft*® CLASSIC, β-TCP granules, which are coated with PLGA) will be mixed in a syringe with the provided BioLinker® (N-methyl-2-pyrrolidone solution, Sunstar) following by instructions by the manufacturer. Graft material will be placed only to coronal to the existing alveolar crest in the sites. After the membrane is tucked on the lingual side with minimal reflection of flap (at

least 3mm over the alveolar crest), the socket orifice with resorbable sutures (5-0 Vycryl). Postoperative instructions will be given, and all patients will be prescribed 500 mg amoxicillin, three times daily for 1 week unless an allergy to penicillin was present, in which case 100 mg doxycycline, once daily for 10 days will be given. All patients will be instructed to rinse for 30 seconds twice daily with alcohol free 0.12% chlorhexidine gluconate (Perodex® Sunstar) for 2 weeks.

Cone beam computed tomography (CBCT) will be obtained from all participants immediate after extraction with ridge preservation procedure as a baseline (T0). CBCT will be obtained with Kodak-9000 (85kV, 1mA, 10.8S) for patient needing one extraction site. If patients need multiple extractions, CBCT will be obtained with i-CAT science international (120kV, 18.54mA, 8.9S). Occlusal and buccal photographs of the surgical site before and after the surgery will be obtained.

Patients will be seen at approximately 1, 2, 4, 12 weeks for follow up visits. Sutures will be removed 2 weeks after the ridge preservation is rendered. Occlusal and buccal photographs of the surgical site will be obtained at every follow up visit. Wound dehiscence and/or membrane exposure will be reported. Adverse events will be recorded. Patients will return approximately 3 months after the extraction for a cone-beam computerized tomographic scan with radiographic stent if patient is receiving implant therapy. Based on the number of CBCT scans taken at baseline, the same number will be taken at this visit. (T1) For those subjects not receiving an implant a follow up CBCT scan will be taken but will not be considered standard of care. New silicone impressions will be taken to evaluate the dimensions of the alveolous before implant placement.

For patients receiving implant therapy, the ridge width and buccal and lingual height will be measured during the implant procedure as described previously. Also during the procedure, a trephine drill with a 2.0mm internal diameter will be used to take a core biopsy up to 8mm in length in the central portion of the alveolar ridge which will be placed in 10% neutral buffered formalin (this procedure is not considered standard of care).

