**Statistical Analyses**

For all treatment group comparisons of bone core percentages and ridge dimensional data, due to the nature of this pilot study, no sample size justification estimated were performed. Means and standard deviations for all parameters will be calculated. The paired-sample t test will be used to assess the statistical significance of the difference between the initial and the 3-month visit within group. Difference will be considered statistically significant at the  $P < .05$ . All data analysis will be performed using statistical software. (Microsoft Excel.)

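### Cast change starts before extraction and CBCT change starts after grafting, so the difference between the two change scores cannot be read as measurement accuracy

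*Combined protocol and SAP*

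**What the plan says.** **Cast baseline (Surgical Protocol).** "Silicone impressions will be taken for all participants prior to extractions". Digital Measurements then defines the cast result as the superimposed difference between pre- and post-treatment casts, read at 1, 3 and 5 mm from the buccal gingival margin on the post-treatment data.

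**CBCT baseline (Surgical Protocol).** The first scan "will be obtained from all participants immediate after extraction with ridge preservation procedure as a baseline (T0"). Material and Methods describes the same scan more briefly, as "taken immediate following extraction to evaluate the dimensions of extracted ridge", and does not mention the graft. CBCT analysis compares baseline with 3 months, at 1, 3 and 5 mm from the T0 crest.

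**Follow-up (Surgical Protocol).** For CBCT: "Patients will return approximately 3 months after the extraction for a cone-beam computerized tomographic scan". For casts: "New silicone impressions will be taken to evaluate the dimensions of the alveolous before implant placement". The second impression is described with the 3-month visit but has no date of its own.

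**Aim (purpose paragraph closing the introduction).** "those dimension change will be measured digitally scanned cast to evaluate the accuracy of the measurements, and cone beam computed tomography".

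**Analysis (Statistical Analyses).** A paired t test of the "difference between the initial and the 3-month visit within group". The section does not say which state counts as initial for each method.

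**The concern.** Extraction, flap, graft and membrane all fall inside the cast interval and outside the CBCT interval. No impression straight after surgery and no CBCT before extraction is described, so the two methods share no starting state.

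The surgical step is plausibly not zero. Inclusion criterion 6 selects sockets in which a buccal dehiscence or fenestration exceeds 50% of the wall height. At surgery the tooth is removed, a flap is raised, graft is placed and a membrane is laid beyond the defect edge. Any of these can alter the buccal contour.

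The cast result answers how the ridge at 3 months compares with the contour while the tooth was in place. The CBCT result answers how much the grafted ridge changed during healing. Both are reported in millimetres at levels labelled 1, 3 and 5 mm, and both would appear as change from an undefined initial visit. A reader who takes the gap between them as measurement error would be attributing an effect of surgery to an instrument.

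**Working it through.** The documents give no figure for this point, so there is nothing of the plan's to reproduce. The check compares timings and then uses a short identity.

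**Timings**

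| | Start | End |
|---|---|---|
| Cast | Before extraction | New impression before implant placement, about 3 months |
| CBCT | After extraction with ridge preservation (T0) | About 3 months (T1) |

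The calendar lengths may be nearly equal. What differs is the starting state.

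**Identity.** Let A be the ridge before extraction, B the ridge after extraction and grafting, and C the ridge at 3 months. Let s be what the cast reading adds because it records the soft-tissue surface and uses a different reference level.

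- Cast change = (C − A) + (s_C − s_A)
- CBCT change = C − B
- Cast minus CBCT = (B − A) + (s_C − s_A) + measurement error

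The term B − A is the surgical step. A common starting state would remove it. The tissue and level terms would remain, because casts are read from the post-treatment gingiva and CBCT from the T0 crest.

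If the shorter Material and Methods wording meant a scan before the graft, B would be replaced by the ungrafted socket. The CBCT change would then include grafting, but its start would still follow extraction while the cast start precedes it.

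**Illustration of size.** All values are assumed. The tissue, level and error terms are set to zero and the post-graft change to −1.2 mm. (The introduction quotes a 1.2 mm width loss from a review of freeze-dried bone allograft; it is not an estimate for this material.)

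| Step B − A (mm) | Cast change (mm) | CBCT change (mm) | Difference (mm) |
|---|---|---|---|
| −1.0 | −2.2 | −1.2 | −1.0 |
| −0.5 | −1.7 | −1.2 | −0.5 |
| 0 | −1.2 | −1.2 | 0 |
| +0.5 | −0.7 | −1.2 | +0.5 |
| +1.0 | −0.2 | −1.2 | +1.0 |

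**If someone tested the difference.** The plan does not do this. Suppose the two change scores were compared by a paired t test with n = 20 (the maximum in Material and Methods), two-sided alpha 0.05 (sidedness assumed) and no bias in either method. With noncentrality = (step / SD) × √20, the chance of a significant difference is:

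| Step (mm) | SD of difference 0.5 mm | 1.0 mm | 1.5 mm |
|---|---|---|---|
| 0 | 5% | 5% | 5% |
| 0.25 | 56% | 19% | 11% |
| 0.5 | 99% | 56% | 29% |
| 1.0 | >99% | 99% | 81% |

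The SDs are also assumed. A modest step could therefore look like disagreement between methods, depending on a spread that the documents do not give.

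**The case against.** **No between-method analysis is planned.** Statistical Analyses specifies means, standard deviations and a within-group paired test. This stands. Each paired test is valid for its own starting state, so the planned tests are not invalidated.

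**The accuracy sentence may not concern cast against CBCT.** The paragraph before it criticises 1 mm probe readings and cites better reproducibility for digital models. The garbled sentence can be read as using casts to overcome probe inaccuracy, with CBCT as a further method. This stands as a possible reading, and nothing names CBCT as the reference standard. But the sentence puts casts, CBCT and accuracy together, so the other reading is open too, and the plan should close it.

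**The baselines are already labelled.** Surgical Protocol does state both timings. Statistical Analyses then uses one undefined word for both, and nothing warns that the changes are not interchangeable.

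**The step is not the only source of difference.** This stands. A reader might infer that with perfect instruments the two changes would differ by exactly the surgical step. The documents do not support that, because tissue and reference level also differ.

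**Opposite signs.** A reader might also infer that the two methods will point in opposite directions. With a loss of 1.5 mm and a step anywhere from −1 to +2 mm (all assumed), the cast change runs from −2.5 to +0.5 mm. It turns positive only when the step exceeds 1.5 mm, the top 0.5 mm of a 3 mm range. Nothing in the documents supports a step that large, so a sign reversal is arithmetically possible and no more.

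**Conclusion.** The concern holds in a limited form. By the timings in Surgical Protocol, the cast change starts before extraction and the CBCT change starts after extraction and grafting. Their difference contains the surgical step, of unknown size and sign, together with tissue and reference-level differences and measurement error. It cannot serve as evidence of accuracy.

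The consequence falls on the accuracy aim in the introduction and on any side-by-side reading of the two results. It does not reach the within-method paired tests. Every millimetre value and percentage above rests on assumed steps, losses and spreads; they show how the identity behaves and do not predict what this study will find. The conclusion about different starting states needs only the stated timings, and holds on either wording of when the first CBCT is taken. The correction is worth making because it is cheap and prevents a wrong conclusion on a stated aim.

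**What to change.** In the purpose paragraph, Digital Measurements and Statistical Analyses:

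1. Define the initial state for each method: cast = pre-extraction to 3 months, net contour change; CBCT = post-graft to 3 months, change of the grafted ridge. Bring the shorter description of the first CBCT in Material and Methods into line with Surgical Protocol.
2. State that these are separate outcomes, and that the difference between the change scores will not be reported as accuracy or measurement error.
3. If a cast-versus-CBCT comparison is wanted, restrict it to 3-month data at a matched level. Digital Measurements specifies only a pre/post difference, so this needs an added absolute reading from the existing 3-month cast. Describe the resulting difference as soft tissue, any remaining level mismatch and measurement error.

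**Cost.** Items 1 and 2 are wording only, with no new visit, scan or impression. Item 3 adds one reading on existing data. The accuracy claim becomes narrower.

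### Does the CBCT provision for patients needing several extractions put the paired t test's unit of analysis in doubt?

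*Combined protocol and SAP*

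**What the plan says.** Material and Methods defines the cohort in the singular: "Up to twenty subjects who have been diagnosed with a need of extraction of single tooth followed by ridge preservation will be recruited". The eligibility list that follows is framed by site ("The following site inclusion criteria will be used"). It asks for a single-rooted tooth, a buccal wall defect of more than half the height, and a further condition, "adjacent teeth to extraction site will be present during healing period". No exclusion criterion bars a patient who needs other teeth removed.

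The Surgical Protocol applies the treatment conditionally, "If the site meets the inclusion criteria", and then gives two CBCT settings. One is "for patient needing one extraction site"; the other begins "If patients need multiple extractions, CBCT will be obtained with i-CAT science international".

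On scan numbers, Material and Methods says that the study procedures "are all within standard care for a tooth extraction with regenerative therapy to preserve the ridge dimensions following extractions with the exceptions of" a short list, whose first item is "The CBCT (one or more) taken immediate following extraction to evaluate the dimensions of extracted ridge". The follow-up text of the Surgical Protocol repeats the baseline number of scans at 3 months. CBCT analysis then describes aligning one baseline and one 3-month data set and measuring three widths (HW1, HW3, HW5) at one socket. Histologic Processing takes one section for each person.

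Statistical Analyses plans means, standard deviations and a paired t test at P < .05. It gives no sample size calculation and does not name the unit of analysis.

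**The concern.** Taken literally, a cohort of single-extraction patients leaves the second CBCT setting with nobody to use it on. Its presence suggests that the authors expected some participants with several extractions. Eligibility is judged by site, and more than one scan per visit is allowed. A second qualifying socket in the same mouth could therefore be grafted, scanned and measured under the text as it stands.

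If such sockets were listed as separate rows, the paired t test would treat two changes from one person as independent. The standard error would then be too small, the P value too low, and the reported n a count of sites rather than subjects. With no more than twenty subjects, even a few double entries might matter. The scan counts also look inconsistent at first: one or more are taken, but only one pair is described in the analysis.

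**Working it through.** **The passages side by side.** Two separate questions are involved.

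*Who enrols.* Material and Methods says one tooth; the Surgical Protocol allows for patients needing several extractions. These can be reconciled if a patient may need several extractions and contribute one study tooth. The documents do not state this, but it fits the rest of the design: one single-rooted tooth in the criteria, one socket in CBCT analysis, one section per person in histology. The CBCT sentence assigns a scanner and exposure settings. It does not say that extra teeth become study sites.

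*How many scans.* There is no contradiction here. Material and Methods and the follow-up text count scans acquired. CBCT analysis says how a baseline/3-month pair is processed. What is missing is a rule for any further scans. The scan count also does not fix the number of values: one scan can show several sockets, several scans can show one socket, and a single pair already yields three widths. Values follow the sockets measured.

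**Size of the effect if second sites were entered as rows.** The plan has no figure of its own to reproduce.

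Inputs from the documents: 20 subjects (the stated maximum) and a significance level of 0.05. Assumptions: two-sided testing; k subjects with two sites each; within-subject correlation of changes (ICC) of 0.2, 0.5 or 0.8; every site entered as an independent row.

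The number of rows is n = 20 + k. The sum of squared sites per subject is (20 − k) + 4k = 20 + 3k. The ratio of the true to the naive standard error is

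ratio = √[(1 − ICC) + ICC × (20 + 3k)/(20 + k)] = √[1 + ICC × 2k/(20 + k)].

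For k = 2: n = 22 and 2k/(20 + k) = 4/22 = 0.182.

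| ICC | ratio² | ratio | effective n = 22/ratio² | simulated type I error |
|---|---|---|---|---|
| 0.2 | 1.036 | 1.018 | 21.2 | 5.4% |
| 0.5 | 1.091 | 1.044 | 20.2 | 6.1% |
| 0.8 | 1.145 | 1.070 | 19.2 | 6.6% |

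A reported P of .05 would correspond to .055, .061 and .067 in these three cases.

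Other values of k, in the same ICC order:
- k = 1: 5.2%, 5.6%, 5.9%
- k = 3: 5.5%, 6.6%, 7.4%
- k = 5: 5.8%, 7.3%, 8.9%
- All 20 subjects with two sites (ICC 0.3, 0.5, 0.8): 8.6%, 11.1%, 15.0%
- 10 subjects, 2 of them with two sites: 5.6%, 6.9%, 8.0%

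With one value per subject, the simulated error is 4.9% to 5.1% throughout.

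**Effect on the descriptive results.** The expected sample variance of the rows is (n − ratio²)/(n − 1) times the true variance. For k = 2 and ICC 0.5 this is (22 − 1.091)/21 = 0.996; over k = 1 to 5 and the three ICCs it runs from 0.987 to 0.999. The mean is unbiased if change is unrelated to the number of sites a person has. The means and standard deviations would therefore hardly move.

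**The case for a change.** The best argument for a change is that it is cheap and the ambiguity is real. Histology has an explicit one-per-person rule, whereas the cast and CBCT measurements do not. Someone screening a patient who needs three teeth removed finds no clear answer. With at most twenty subjects and no sample size basis, readers should be able to see whether n counts people or sockets. The number of two-site subjects is also unknown, and at the extreme, with two sites in everyone, the error would be far from 5%.

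Much of this stands. The enrolment wording is inconsistent, the unit is unnamed, and no document figure caps the number of two-site subjects. The step from there to a flawed analysis does not stand. It requires that extra teeth become study sites, that they qualify, and that they are entered as independent rows; the plan says none of these. The adjacent-teeth condition rules out neighbouring sockets, and the tooth and defect criteria narrow the field further, although by how much cannot be given a figure. The extreme case would also contradict the stated recruitment of single-tooth patients outright.

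**Conclusion.** No change to the analysis is needed. One wording conflict exists: single-tooth recruitment against a scanner setting for multiple extractions. There is also an unstated unit of analysis and no rule for surplus scans. These are gaps in description that an analyst fills in the obvious way, with one study tooth and one change per outcome for each subject. On that basis the paired t test has at most 20 pairs, 19 degrees of freedom and its nominal 5% level.

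The departure from that reading is hypothetical. With one or two two-site subjects among 20, the type I error would be about 5.2% to 6.6% at ICC 0.2 to 0.8. Larger figures need more two-site subjects than the recruitment statement suggests. The P value also carries little weight in this study. It is an uncontrolled pilot case series, its introduction already accepts that grafting cannot fully prevent bone loss, and its useful results are means and standard deviations that would be almost unaffected. The conclusion rests on the single-tooth reading of Material and Methods; the number of two-site subjects, the ICC and two-sided testing are assumptions, not document figures.
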